10.4.4. Clinician- and Patient-reported Outcomes

10.4.4.1. Patient-Reported Outcomes Measurement Information System

The Patient-Reported Outcomes Measurement Information System (PROMIS) was developed by the National Institutes of Health and uses domain-specific measures to assess patient well-being ([NIH, 2015](#); [Broderick et al., 2013](#)). The domain-specific approach is based on the idea that health attributes, such as pain and physical function are not unique to a specific disease. PROMIS Fatigue, Pain Interference, Physical Function, and Global Heath scales will be administered.

The PROMIS questionnaires will be completed at time points specified in [Table 4](#), [Table 5](#), and [Table 6](#). The PROMIS questionnaires should be completed within a week prior to dosing visits. Additional details regarding the PROMIS questionnaires are available in the Clinical Evaluator Manual.

10.4.4.2. 36-item Short-Form Health Survey

The 36-item Short-Form Health Survey version 2 (SF-36v2) health survey captures practical, reliable, and valid information about functional health and well-being from the subject's perspective. The SF-36v2 is a 36-item, self-reported questionnaire designed to assess health-related quality of life in healthy and ill individuals. Specifically, the SF-36v2 assesses physical and mental health based on 8 scaled scores that are the weighted sums of the questions in their section: vitality, physical functioning, bodily pain, general health perceptions, physical role functioning, emotional role functioning, social role functioning, and mental health. Each scale is directly transformed into a 0 to 100 scale on the assumption that each question carries

equal weight. Lower scores indicate more disability, and higher scores indicate less disability, ie, a score of zero is equivalent to maximum disability and a score of 100 is equivalent to no disability.

The SF-36v2 will be completed at time points specified in [Table 4](#), [Table 5](#), and [Table 6](#). The SF-36v2 should be completed within a week prior to dosing visits. Additional details regarding the SF-36v2 are available in the Clinical Evaluator Manual.

10.4.4.3. GNE Myopathy Functional Activities Scale Expanded Version

The GNE Myopathy Functional Activities Scale (GNEM-FAS; also referred to as HIBM-FAS in some studies) was designed to assess the functional impact of changes in muscle strength in GNE myopathy and similar diseases ([Mayhew et al., 2017](#); [Skrinar et al., 2013](#)). The scale consists of 3 domains: mobility, upper extremity, and self-care; scores for each domain and a total score will be obtained. Items in the scale assess the subject's ability to independently perform various activities of living that involve self-care, mobility and use of the upper and lower extremities. The original GNEM-FAS was developed for ambulatory patients with GNE myopathy but has since been modified to include additional items to accommodate weaker patients. This modified version is referred to as the GNEM-FAS expanded version and will be used in this study. The scale will be administered by a clinician trained by Ultragenyx (licensed physical therapist, unless approved by Ultragenyx). Training must be completed successfully prior to assessing any subject for the study. The clinicians' role is a combination of observing subjects conducting activities and asking subjects questions to assess performance of these activities.

The GNEM-FAS expanded version will be assessed at time points specified in [Table 4](#), [Table 5](#), and [Table 6](#). The GNEM-FAS expanded version should be completed within a week prior to dosing visits. Additional details regarding the GNEM-FAS expanded version are available in the Clinical Evaluator Manual.

10.4.4.4. Nutrition Diary

Subjects will be asked to maintain a record of daily diet using a diary at time points specified in [Table 4](#), [Table 5](#), and [Table 6](#). For all cohorts, the nutrition diary recordings should be recorded at least 3 consecutive days per week through screening or rescreening, as applicable, and for the 3 consecutive days in the week leading up to each subsequent visit. Qualified Investigator site staff should review nutrition diary data at each visit. Additional details regarding the nutrition diary are available in the Study Reference Manual.

10.5. Pharmacodynamic and Biomarker Assessments

10.5.1. Controlled Fasting Challenge

In RD cohorts, the subject's ability to maintain symptom-free euglycemia during an optional CFC at select sites for select subjects will be assessed at the STV and Week 16 (OL-RD Cohorts) or Week 10 (DB-RD Cohorts) Visits; only subjects who completed the optional CFC at STV complete the CFC at Week 16 or 10. The CFC can be conducted at the hospital during the day or an overnight stay, but the time of day should be consistent within subjects between the STV and Week 16 or Week 10 assessment. For a daytime CFC, an overnight stay in the hospital the night

before might be needed. With either a daytime or overnight CFC, it is critical that appropriate personnel are present to monitor the subject during the CFC and to provide rescue treatment if needed. Special attention should be provided during nursing shift changes.

Before the CFC is conducted, morning cortisol is collected between 6 and 9 am and analyzed by the central lab. This collection can occur on the morning of the CFC or, for the STV CFC, anytime between the ISV and STV. For subjects with suspected hypothalamic-pituitary axis (HPA) dysfunction (eg, those with a history of prolonged steroid treatment), morning cortisol should be reviewed by the Investigator and discussed with the Medical Monitor before deciding if it is safe to conduct the CFC. In this scenario, the morning cortisol sample should be collected at least a week prior to the CFC, providing sufficient time to review the lab results.

Before the CFC begins, a venous catheter is placed for serial blood sampling and to allow for provision of a rescue glucose infusion if needed. A venous blood sample for measurement of glucose, cortisol, glucagon, insulin, C-peptide, and β -hydroxybutyrate will be collected at the beginning (ie, immediately after the provided meal or cornstarch, as applicable, described below), at end of the CFC, and 30 minutes after the end of the CFC. These samples will be sent to a central lab, except glucose which will be analyzed by the local lab.

During the CFC, venous blood samples for STAT analysis of glucose will be collected through an indwelling catheter every 60 minutes (\pm 5 minutes) until the venous glucose level decreases to \leq 70 mg/dL (\leq 3.9 mmol/L). Thereafter, venous blood glucose is measured approximately every 30 minutes (\pm 5 minutes) until the end of the CFC. Venous blood glucose taken during the CFC will be analyzed locally and available within 30 minutes to ensure subject safety. Capillary glucose and ketone measurements using an HHG and ketone meter will also be performed during the CFC at the same time as venous blood glucose or more frequently as needed.

The CFC will end when the subject's glucose level decreases to $<$ 54 mg/dL ($<$ 3.0 mmol/L), when the subject experiences signs and symptoms of hypoglycemia, or the fast reaches 12 (daytime) or 15 (overnight) hours without hypoglycemia, whichever occurs first. During the CFC, subjects may drink water, but cannot ingest any other food or drink. The start and end times of the CFC will be recorded in EDC.

Data from the HHG will be uploaded via the study provided laptop. Data from venous blood glucose and capillary ketones taken during the CFC will be entered into the EDC. Subjects should continue to wear their CGM device throughout the fasting challenge. Readings from the CGM device during the CFC may alert the site to a potentially low glucose value that would require confirmation by capillary and venous blood glucose.

At the end of the CFC, the subject's hypoglycemia should be treated per the institution's standard procedure, which may include providing the subject with a meal, cornstarch, or IV glucose, if medically indicated.

Daytime CFC

If the CFC is conducted during the day, the study site will provide breakfast for the subject. The breakfast meal will be personalized for each subject and will include a target carbohydrate range that should be as close as possible to the subject's usual breakfast meal based on their current nutrition prescription; for the Week 16 (OL-RD Cohorts) or 10 (DB-RD Cohorts) CFC, the breakfast meal will be identical to the breakfast consumed for the STV CFC. Subjects will be

instructed to consume the entire breakfast meal and minimize activity after they finish eating breakfast until the end of the CFC. Breakfast meal stop time and its full nutrient composition will be recorded by the subject in the nutrition diary with the assistance of the study dietitian as needed. If a subject is taking a morning dose of cornstarch or protein supplement with breakfast, they will be given their usual morning dose at the usual time but no more than 4 hours after breakfast. The amount of cornstarch and protein to administer at the Week 16 or 10 CFC should be the same as what the subject received at their STV CFC. The time and amount will also be recorded by the subject in the nutrition diary with the assistance of the study dietitian as needed. The CFC starts when the subject finishes breakfast and the associated cornstarch and/or protein dose, as applicable.

Overnight CFC

If the CFC is conducted overnight, the study site will provide dinner for the subject. The dinner meal will be personalized for each subject and will include a target carbohydrate range that should be as close as possible to the subject's usual dinner meal based on current nutrition prescription. for the Week 16 (OL-RD Cohorts) or 10 (DB-RD Cohorts) CFC, the dinner meal will be identical to that of the STV CFC. Subjects will be instructed to consume the entire dinner meal and minimize activity after they finish eating dinner until the end of the CFC. Dinner meal stop time and its full nutrient composition will be recorded by the subject in the nutrition diary with the assistance of the study dietitian as needed. If a subject is taking cornstarch or protein supplement, they will be given their usual oral dose at the usual time but no more than 4 hours after dinner. The amount of cornstarch and/or protein to administer at the Week 16 or 10 CFC should be the same as what the subject received at their STV CFC. The time and amount will also be recorded by the subject in the nutrition diary with the assistance of the study dietitian as needed. If a subject does not receive cornstarch or protein supplement before going to bed, the CFC starts when the subject finishes dinner. The CFC starts when the subject finishes dinner and the associated cornstarch and/or protein dose, as applicable.

10.5.2. Ketones

In addition to urine ketones assessed in urinalysis (Section 10.1.5 and Appendix 3), blood (serum for SAD cohorts and capillary for RD cohorts) will be analyzed to evaluate the PD effect of UX053 on ketosis at specified time points in [Table 4](#), [Table 5](#), and [Table 6](#). For visits in which subjects are receiving study drug, blood or capillary measurements will be collected prior to dosing.

10.5.3. Continuous Glucose Monitoring

At the Screening Visit for the SAD cohort and ISV for the DB-RD cohort, each subject will receive a CGM and HHG device and be trained on how to use the device. For SAD cohorts, the CGM device will be worn from the Screening Visit until the End of Study (EOS) I D90/ET Visit ([Table 4](#)). For OL-RD cohorts, the continual glucose monitor will be worn from the OL-RD rescreening ISV to the Week 24 Visit, and for the week prior to the Week 36 and EOS II W48/ET Visits ([Table 5](#)). For DB-RD cohorts, the CGM will be worn for from ISV to the Week 24 Visit, and for the week prior to the Week 36 and EOS III W48/ET Visits ([Table 6](#)).

If the CGM device alarm notifies a subject that their blood sugar is abnormally high or low or the subject suspects their blood sugar is abnormally high or low, the subject will need to check their

blood sugar with a HHG that will be provided by Ultragenyx during screening (or rescreening, as applicable). If action is taken to rectify abnormal blood glucose levels, the event should be recorded as an AE ([Appendix 1](#) and [Appendix 2](#)).

When CGM data is being collected, all subjects will connect their CGM and HHG devices to a study-provided laptop weekly and upload CGM and HHG data. At remote visits, in conjunction with assessments performed by a home health nurse, the site will contact subjects by telephone or videoconference to confirm the CGM device is properly in use and data was uploaded; answer any questions regarding or help troubleshoot (if necessary) CGM device use; and review CGM data, HHG data (when applicable), and nutrition diary entries; outside of scheduled visits, these telephone calls will occur as needed. At in-clinic visits, a conversation between the site and the subject should occur to ensure CGM compliance and troubleshoot if needed.

Additional details regarding the CGM device are available in the Study Reference Manual.

10.5.4. Hemoglobin A1C

Hemoglobin A1C integrates average blood glucose over a 3-month period and can be used to monitor more chronic changes in blood glucose. Blood will be collected to measure hemoglobin A1C at specified time points in [Table 4](#), [Table 5](#), and [Table 6](#). Samples will be processed by a central lab to ensure consistency across study sites.

10.5.5. Glucose Tetrasaccharide

Glc₄ is a limit dextrin of the glucose polymer amylopectin and is elevated in GSD III ([Halaby et al., 2019](#)).

Urine will be collected for assessment of Glc₄ to evaluate a biomarker of disease activity in GSD III at specified time points in [Table 4](#), [Table 5](#), and [Table 6](#). All efforts should be made for urine collection to be consistently taken from the first morning void.

10.5.6. *AGL* Gene Sequencing

Blood will be collected for *AGL* mutation analysis for all qualified subjects, even if the subject or a family member has a confirmed *AGL* mutation, at time points in [Table 4](#) and [Table 6](#). For each subject, both alleles of the *AGL* gene will be analyzed by a central laboratory for known pathogenic or likely pathogenic mutations. Results will be used for research purposes to better understand the genotype-phenotype relationships in affected individuals with GSD III.

10.5.7. Exploratory Future Use of Blood

Blood will be collected and processed into serum, plasma, white blood cells, and red blood cells for optional, non-protocol-required additional future research at time points in [Table 4](#), [Table 5](#), and [Table 6](#). These additional samples will be used to assess novel emerging biomarkers of GSD III and/or UX053 and the relationship to GSD III presentation or prognosis. For visits in which subjects are receiving study drug, blood will be collected prior to dosing.

10.6. Appropriateness of Measurements

This is a FIH study designed to assess the safety, PK, PD, and preliminary efficacy of UX053 in patients with GSD III. The safety parameters to be evaluated in this study include standard assessments such as recording of medical history, AEs, SAEs, physical examination, vital signs, serum chemistry, concomitant medications, and other clinical and laboratory procedures.

The efficacy endpoints to be evaluated in this study examine liver health, cardiac health, muscle health, strength, and patient- and clinician-reported outcomes. Exploratory assessments include potential biomarkers of disease activity that can be used to monitor PD effects of UX053.

These efficacy and exploratory assessments are standard measures used to identify, assess, and monitor the signs and symptoms of GSD III. Where possible, timing of assessments has been coordinated with standard safety laboratory tests to minimize risk of discomfort and avoid unnecessary duplication of testing. Nutrition diaries will also be used to characterize disease management and monitor care throughout the study.

11. STATISTICAL CONSIDERATIONS

A full description of the analysis details will be provided in the SAP.

11.1. Sample Size Determination

The sample size for this study is based on practical considerations and is consistent with a FIH study in a rare disease population. The study plans to enroll approximately 18 subjects (assuming Cohorts 1-3S and DB-1-3R are initiated), with a minimum of 6 subjects in the SAD cohorts and 12 subjects in the DB-RD cohorts, with the option to enroll additional subjects in any cohort to further characterize safety or PD findings. With at least 6 subjects receiving UX053 in the SAD cohorts, there is an 74% chance of detecting a more common AE given the TEAE has a true incidence of 20%. If at least 18 subjects receive UX053 in both SAD and RD cohorts, there is an 85% chance of detecting a TEAE with true incidence of 10%.

Subjects will be replaced at Ultragenyx's discretion only if they have not received study drug. Subjects will not be replaced if they have received any study drug.

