7. INVESTIGATIONAL PLAN

7.1. Study Design

UX053-CL101 is a phase 1/2 FIH study to evaluate the safety, tolerability, and PK of SAD and RD of UX053 in patients with GSD III ([Figure 1](#)). The SAD cohorts will be OL. There will be 2 types of RD cohorts: 1) OL-RD and 2) randomized, DB, and placebo-controlled RD (referred to as DB-RD). Treatment-naïve subjects enter the SAD and DB-RD cohorts. Subjects in the SAD cohorts who complete the 90-day Follow-up Period can enter OL-RD cohorts. Details for each of these cohorts are described below.

Single Ascending Dose Cohorts

The SAD cohorts evaluate safety and PK of single doses of UX053 in treatment-naïve subjects. All subjects in the SAD cohorts will undergo a Screening Visit prior to their Baseline Visit. There are 3 planned SAD cohorts, each consisting of at least 2 subjects, all of whom will receive open-label UX053 ([Figure 1](#)). The planned dose escalation will proceed from 0.05 mg/kg in Cohort 1S, to 0.10 mg/kg in Cohort 2S, and to 0.20 mg/kg in Cohort 3S. An independent DMC will review at least 2 weeks of safety data for at least 2 subjects within a SAD cohort and the cumulative data from all subjects in prior dosing cohorts (when applicable) before deciding to proceed with the next SAD cohort.

Each subject in the SAD cohorts will be followed for a follow-up of 90 days after dosing. At the SAD Day 90 Visit, marking completion of the follow-up, subjects can be rescreened for entry into the OL-RD cohorts described below.

Open-Label Repeat Dosing Cohorts (Extension for SAD Cohorts)

The OL-RD cohorts serve as a short-term extension for subjects who participated in a SAD cohort. The OL-RD cohorts evaluate the safety and PK of 4 additional OL doses of UX053 in subjects who received a single dose of UX053 in a SAD cohort and completed the 90-day Follow-up Period. Subjects from the SAD cohorts are rescreened for participation in the OL-RD cohorts; eligibility for additional dosing in the OL-RD cohorts can be combined with assessments at the SAD Day 90 Visit.

During rescreening, a nutrition assessment will be completed at an Initial Screening Visit (ISV) to determine if the subject's diet meets the nutritional guidelines for adults with GSD III based on expert recommendations ([Table 2](#)). OL-RD subjects will proceed through rescreening as shown in [Figure 2](#) based on whether they meet these nutritional guidelines.

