For selected sites and subjects, the DB-RD STV includes an optional controlled fasting challenge (CFC). Prior to the CFC, a morning cortisol is obtained between 6 and 9 am. The CFC is conducted during the subject's stay in the hospital, usually overnight, but can be conducted during the day. For the same sites and subjects, another optional CFC occurs at the Week 10 Visit; only subjects who completed the optional CFC at STV complete the CFC at Week 10. Additional details regarding the CFC are in Section [10.5.1](#).

In DB-RD cohorts, treatment-naive subjects will be randomized 3:1 to UX053 or placebo in ascending dose cohorts (4 subjects per cohort) ([Figure 1](#)). DB-RD subjects will receive study drug Q2W; a total of 5 doses of study drug are planned. The planned dose levels are 0.05 mg/kg in cohort DB-1R, 0.10 mg/kg in cohort DB-2R, and 0.20 mg/kg in cohort DB-3R.

Initiation of RD Cohorts (Both OL-RD and DB-RD)

Initiation of RD cohorts is as follows:

- Initiation of Cohort DB-1R and OL-1R will be guided by DMC review of at least 2 weeks of safety data from at least 2 Cohort 2S subjects and any available data from all subjects in prior and ongoing cohorts.
- Initiation of Cohort OL-2R and DB-2R will be guided by DMC review of either 1) at least 6 weeks of safety data from at least 4 subjects within Cohort DB-1R or 2) at least 12 weeks of safety data from at least 3 subjects within Cohort OL-1R (whichever is available first). In both of these scenarios, all available data from all subjects in prior and ongoing cohorts will also be reviewed.
- Initiation of Cohort OL-3R and Cohort DB-3R will be guided by DMC review of either 1) at least 6 weeks of safety data from at least 4 subjects within Cohort DB-2R or 2) at least 12 weeks of safety data from at least 3 subjects within Cohort OL-2R (whichever is available first). In both of these scenarios, all available data from all subjects in prior and ongoing cohorts will also be reviewed.

Cohort- and Subject-level Dose Selection and Modification for All Cohorts (SAD, OL-RD, and DB-RD)

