7.1.2. Number of Subjects

Approximately 18 adult subjects are planned to be enrolled. Additional subjects may be enrolled to further characterize safety.

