3.5 Sample Size Considerations

The sample size for this study is based on practical considerations and is consistent with a FIH study in a rare disease population. Approximately 26 to 30 subjects will enroll in this study, with a minimum of 10 subjects in the SAD period, 16 subjects in the RD period, and with the option to enroll additional subjects in any cohort to further characterize safety or PD findings. With at least 10 subjects receiving UX053 in the SAD Period, there is an 89% chance of detecting a more common AE given the TEAE has a true incidence of 20%. If at least 22 subjects receive UX053 in both SAD and RD Periods, there is a 90% chance of detecting a TEAE with true incidence of 10%.

Subjects will be replaced at Ultragenyx's discretion only if they have not received study drug. Subjects will not be replaced if they have received any study drug.

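### The 85% detection figure in Protocol 11.1 assumes 18 subjects on UX053, but 18 is total planned enrolment including placebo; the planned minimum treats 15, which gives 79%

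*Protocol*

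**What the plan says.** Protocol 11.1 (Sample Size Determination) plans about 18 subjects, "with a minimum of 6 subjects in the SAD cohorts and 12 subjects in the DB-RD cohorts". Section 7.1.2 gives the same total: "Approximately 18 adult subjects are planned to be enrolled". Both sections allow further subjects, but neither commits to a number.

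Section 11.1 then gives two detection probabilities. The first is for the SAD cohorts alone: 6 treated subjects, true incidence 20%, 74%. The second is for SAD and RD together: "If at least 18 subjects receive UX053 in both SAD and RD cohorts, there is an 85% chance of detecting a TEAE" of true incidence 10%.

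Protocol 7.1 (Study Design) determines who receives UX053:

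- SAD: "There are 3 planned SAD cohorts, each consisting of at least 2 subjects, all of whom will receive open-label UX053".
- DB-RD: "treatment-naive subjects will be randomized 3:1 to UX053 or placebo in ascending dose cohorts (4 subjects per cohort", with three planned cohorts.
- OL-RD: "4 additional OL doses of UX053 in subjects who received a single dose of UX053 in a SAD cohort".

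**The concern.** The number treated in the second probability statement equals the total to be enrolled. Since the DB-RD cohorts include placebo, the two numbers cannot coincide at the planned minimum. It appears that the placebo subjects were not taken out.

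Two features suggest that the 18 is meant to describe the plan and is not a free-standing example. The sentence just before it uses the planned SAD minimum of 6. The SAP's version of the same pair of statements (section 3.5), written for an earlier and larger design, uses a number treated that is net of placebo.

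Safety is the primary objective, and section 11.1 is where the protocol says what its size can show about safety. An ethics committee, regulator or investigator would conclude that the planned study has an 85% chance of showing a 10% adverse event at least once.

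**Working it through.** **Method.** The chance of at least one event among n treated subjects, with true incidence p, is 1 − (1 − p)^n. No alpha, margin or dropout enters.

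**Reproducing the stated figures**

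| Source | n treated | p | 1 − (1 − p)^n | Stated |
|---|---|---|---|---|
| Protocol 11.1, SAD | 6 | 0.20 | 1 − 0.8^6 = 73.8% | 74% |
| Protocol 11.1, SAD and RD | 18 | 0.10 | 1 − 0.9^18 = 85.0% | 85% |
| SAP 3.5, SAD | 10 | 0.20 | 1 − 0.8^10 = 89.3% | 89% |
| SAP 3.5, SAD and RD | 22 | 0.10 | 1 − 0.9^22 = 90.2% | 90% |

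All four reproduce. The question is only whether n is right for the design.

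**Counting UX053 exposure at the protocol's planned minimum**

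- SAD: 3 cohorts × 2 = 6, all on UX053.
- DB-RD: 3 cohorts × 4 = 12 at 3:1, so 12 × 3/4 = 9 on UX053 and 3 on placebo.
- OL-RD: former SAD subjects, so 0 newly exposed.
- Total on UX053: 6 + 9 = 15. Total enrolled: 6 + 12 = 18.

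**The same count for the SAP's design.** The SAP plans "with a minimum of 10 subjects in the SAD period, 16 subjects in the RD period". On UX053 that is 10 + 16 × 3/4 = 22, the number its statement uses. The 4 placebo subjects are excluded there.

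**Result with the correct n**

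| n treated | Chance of seeing a 10% event | Chance of missing it |
|---|---|---|
| 15 (planned minimum) | 1 − 0.9^15 = 79.4% | 20.6% |
| 16 | 81.5% | 18.5% |
| 17 | 83.3% | 16.7% |
| 18 (stated) | 85.0% | 15.0% |

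The same gap can be put in two other ways:

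- With 15 treated, an 85% chance applies to an incidence of 1 − 0.15^(1/15) = 11.9%.
- If no event is seen, the one-sided 95% upper bound on incidence is 1 − 0.05^(1/15) = 18.1% with 15 treated, against 1 − 0.05^(1/18) = 15.3% with 18.

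**The case against.** The strongest reply is that the sentence is a true conditional. It begins with an if, it is correct for 18 treated subjects, and the protocol never says that the minimum design treats 18. On that view this is a matter of clarity, not an arithmetical error.

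The reply continues that exceeding the minimum is a real part of the design. SAD cohorts have at least 2 subjects, any cohort may be enlarged, and further cohorts may be added. One route for opening the next RD dose level needs at least 3 subjects in an OL-RD cohort, and those subjects can come only from SAD. SAP section 8 reports that 4 subjects were in fact enrolled in each of Cohorts 1S and 2S. With 2 in Cohort 3S and 9 active DB-RD subjects, that would have made 4 + 4 + 2 + 9 = 19 treated, and 1 − 0.9^19 = 86.5%.

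Finally, nothing depends on the figure. The sample size is practical, the analyses are descriptive, and the study ended after those 8 SAD subjects.

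Much of this stands. The sentence is not literally false, 18 treated could have been reached, and the practical consequence is small. It does not remove the point. The extra subjects are optional and unnumbered, and what was enrolled later is not the plan that section 11.1 describes. The companion sentence uses the planned minimum, and the SAP's parallel sentence subtracts placebo. Read in that setting, the sentence credits the planned size with a property that it does not have.

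**Conclusion.** The concern holds. At the planned minimum, 15 subjects receive UX053, and the chance of detecting a TEAE of 10% incidence is 79.4%, about 5.6 percentage points below the stated 85%.

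This rests on the protocol's own minimum counts, on exact 3:1 allocation within each DB-RD cohort of 4, and on every enrolled subject being dosed. The 74% figure for SAD alone is correct, as are both SAP figures for the SAP's own design.

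The matter is worth correcting because it concerns the primary objective and could be carried into a report or a later protocol. It affects no conduct or analysis in this study, which SAP section 8 says terminated with 8 SAD subjects.

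**What to change.** In Protocol 11.1, replace the second probability statement with one tied to planned exposure, for example: *With at least 15 subjects receiving UX053 (6 in SAD and 9 in DB-RD), the chance of observing at least one case of a TEAE with a true incidence of 10% is 79%.*

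If the 85% figure is to be kept as well, say that it needs 18 UX053-treated subjects, three more than the planned minimum, and therefore more than 18 enrolled (at least 21, if all three were added in SAD).

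The cost is one sentence and a slightly less favourable number. No subjects are added and no analysis changes.
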